#### 8.6 Subsequent Assessments

Participants randomised to the intervention will be followed-up on a weekly basis by the investigator with a telephone call to troubleshoot any problems arising with software/cognitive training program, or any changes in circumstance that would preclude ongoing study involvement. Participants will be followed up after 8-12 weeks of cognitive training, and will return to the CHIASM laboratory to repeat the baseline assessments (cognition (ACE-III), mood (GDS-15), function/ADLs (Lawton-IADL), quality of life (DEMQOL), neurovascular function (TCD), blood pressure (Finometer), heart rate (3 lead ECG) and end-tidal CO2 (ETCO2, capnography, nasal speculum). Adverse events will also be assessed at this time point.

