## 6. STUDY DESIGN

### 6.1 Summary of Trial Design

This is a prospective, feasibility, RCT of CT in healthy older adults, and adults with AzD, MCI, or post-ischaemic stroke. This trial is un-blinded, due to the nature of the intervention. The expected duration of participation per individual is three to six months. Initially, participants will be approached by a member of the clinical care team or research support staff, who will screen and identify eligible participants. Study specific information will then be provided by the researcher. Following this, participants will undergo informed consent. Each participant will have two visits (initial and follow-up assessment). After the first visit, participants will be randomised to control or intervention (CT), and will complete an 8-12 week CT program, if selected for the intervention group. Participants will be randomised using Sealed Envelope ©, an online, commercially available randomisation tool. At the end of the trial, participants will be given the option to participate in a qualitative study by semi-structured interviews or focus group. A flow chart for this process can be seen in Appendix A.

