### 10.2 Reporting Procedures for All Adverse Events

All AEs occurring during the study observed by the investigator or reported by the participant, whether or not attributed to study, will be recorded on the CRF.

The following information will be recorded: description, date of onset and end date, severity, assessment of relatedness to study, other suspect device and action taken. Follow-up information should be provided as necessary.

AEs considered related to the study as judged by a medically qualified investigator or the sponsor will be followed until resolution or the event is considered stable. All related AEs that result in a participant's withdrawal from the study or are present at the end of the study, should be followed up until a satisfactory resolution occurs. It will be left to the investigator's clinical judgment whether or not an AE is of sufficient severity to require the participant's removal from the study. A participant may also

voluntarily withdraw from the study due to what he or she perceives as an intolerable AE.

The severity of events will be assessed on the following scale: 1 = mild, 2 = moderate, 3 = severe.

The relationship of AEs to the study will be assessed by a medically qualified investigator.

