### **16.2 Data Safety Monitoring Committee (DSMC)**

As this is a non-pharmacological feasibility RCT, a DSMC is not required, but adverse events will be reviewed at TSC meetings.

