## APPENDIX A: PATIENT RECRUITMENT FLOW CHART

**20. APPENDIX B: STUDY FLOWCHART**

## 21. APPENDIX C: SCHEDULE OF PROCEDURES

Procedures	Visits				Windows
	Screening	Baseline	Follow-up	Qualitative arm	
Informed consent	x			x	1 month
Screening MoCA	x				1 month
Demographics	x	x		x (carers)	1 month
Medical history	x	x			1 month
Concomitant medications	x	x			1 month
Eligibility assessment	x				N/A
Randomisation		x			4-6 weeks
Compliance		x	x		N/A
Cognition (ACE-III)		x	x		Baseline: 4-6 weeks, Follow-up: 8-12 weeks from randomisation
Mood (GDS)		x	x		Baseline: 1 month, Follow-up: 8-12 weeks from randomisation
Edinburgh handedness Inventory		x			Baseline: 1 month, Follow-up: 8-12 weeks from randomisation
Function (Lawton-IADL)		x	x		Baseline: 1 month, Follow-up: 8-12 weeks from randomisation
Quality of Life (DEMQOL)		x	x		Baseline: 1 month, Follow-up: 8-12 weeks from randomisation
Neurovascular function (TCD, blood pressure, ECG, ETCO 2 )		x	x		Baseline: 4-6 weeks, Follow-up: 8-12 weeks from randomisation
Adverse event assessments			x		N/A

Telephone Support (intervention arm only)		x	x		Weekly telephone support to participants in intervention arm.
Qualitative interview/focus group (optional)				x	At least 1 week after trial completion

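### Adverse events are liable to be ascertained unequally by arm, because only the training arm has scheduled contact between the two visits

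*Combined protocol and SAP*

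**What the plan says.** Section 6.1 gives each participant two visits, initial and follow-up. Section 8.6 adds, for one arm, a schedule of calls: "Participants randomised to the intervention will be followed-up on a weekly basis by the investigator with a telephone call". Their stated purpose is "to troubleshoot any problems arising with software/cognitive training program, or any changes in circumstance that would preclude ongoing study involvement". Appendix C repeats the restriction in a row labelled as intervention arm only: "Weekly telephone support to participants in intervention arm". No passage gives controls a matching contact.

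The only scheduled AE assessment is at the follow-up visit. Section 8.6 says of that visit: "Adverse events will also be assessed at this time point". The AE row of Appendix C is marked at follow-up only and carries no arm restriction.

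The rule for CRF entries in section 10.2 is wider than that assessment: "All AEs occurring during the study observed by the investigator or reported by the participant, whether or not attributed to study, will be recorded". It does not depend on the event having been elicited at a visit. Section 10.2 lists the items to be recorded for each AE; how the event came to light is not among them.

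Section 8.5 states that the investigator makes the calls, takes the baseline and follow-up measurements, and cannot be blinded. Section 16.2 says there is no data safety monitoring committee but that "adverse events will be reviewed at TSC meetings".

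**The concern.** An event mentioned on a weekly call has to be recorded under section 10.2. The same event in a control enters the data only if the participant volunteers it or recalls it at follow-up, 8-12 weeks after randomisation. That recall is a weak instrument in this population: section 7.2 admits people with MCI or Alzheimer's disease with MoCA scores down to 9. Analysing a batch-anonymised data set, as section 8.5 plans, cannot repair events that were never collected.

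Withdrawal adds to the imbalance. Under section 8.9 withdrawn participants need not attend further assessments. A control who withdraws for a reason other than an AE may never be asked about AEs, while a trainee may already have mentioned events by telephone.

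At stake is how the descriptive safety data are read. Section 16.1 has the TSC assess safety or adverse outcomes. If counts are laid out by arm, an excess produced by extra opportunity to report could be taken for an effect of training.

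**Working it through.** The documents give no AE rate, detection probability or AE comparison, so there is no stated figure to reproduce. The check has three parts.

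**1. Scheduled contacts after baseline at which an AE could be mentioned**

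- Training: 8-12 weekly calls (sections 8.6 and 9.1) plus one follow-up visit, so 9-13.
- Control: one follow-up visit, so 1.

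The total number of extra calls depends on arm size. The synopsis gives 80 participants; section 11.2 gives 60. No allocation ratio is stated, so 1:1 is an assumption.

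- 60 participants: 30 × 8 = 240 to 30 × 12 = 360 calls.
- 80 participants: 40 × 8 = 320 to 40 × 12 = 480 calls.

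The range is about 240-480. These counts describe the imbalance; they do not enter the ratio below.

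**2. Effect on recorded rates when the true risk is the same in both arms**

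Let p be the true risk, v the probability that an event is captured at the follow-up visit, and q the probability that an event missed there was captured on a call. Assume for now that controls report nothing between visits.

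- Control recorded rate = p × v
- Training recorded rate = p × [1 − (1 − v)(1 − q)]
- Ratio = [1 − (1 − v)(1 − q)] / v, which does not depend on p

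Both v and q are assumed, over v = 0.3 to 0.7 and q = 0.1 to 0.3:

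| v | q | Training capture | Ratio |
|---|---|---|---|
| 0.7 | 0.1 | 1 − 0.3 × 0.9 = 0.73 | 0.73 / 0.7 = 1.04 |
| 0.7 | 0.3 | 1 − 0.3 × 0.7 = 0.79 | 0.79 / 0.7 = 1.13 |
| 0.3 | 0.1 | 1 − 0.7 × 0.9 = 0.37 | 0.37 / 0.3 = 1.23 |
| 0.3 | 0.3 | 1 − 0.7 × 0.7 = 0.51 | 0.51 / 0.3 = 1.70 |

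Other assumed ranges (v = 0.5 to 0.9, q = 0.25 to 0.8) give 1.03 to 1.80. With good recall at follow-up the ratio is close to 1.

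In participants, taking an assumed p = 0.4 and 30-40 per arm:

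- v = 0.7, q = 0.1: 0.4 × (0.73 − 0.70) = 0.012, or 0.4 to 0.5 extra participants with a recorded event.
- v = 0.3, q = 0.3: 0.4 × (0.51 − 0.30) = 0.084, or 2.5 to 3.4 extra.

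**3. Allowing controls to report between visits**

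Let s be the probability that a control spontaneously reports an event that the visit would miss, and let q now cover all between-visit capture in the training arm. The ratio becomes [1 − (1 − v)(1 − q)] / [1 − (1 − v)(1 − s)]. With q = 0.3 and s = 0.1:

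- v = 0.3: 0.51 / 0.37 = 1.38
- v = 0.7: 0.79 / 0.73 = 1.08

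Spontaneous reporting narrows the gap. It closes only if s reaches q, that is, if unprompted controls report as much as participants telephoned every week.

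**The case against.** The strongest reply is that nothing in the plan depends on this. AEs are not among the endpoints in section 6.2, and section 11 plans no AE table, rate or test by arm. The formal AE assessment falls once, at the same visit, in both arms. The calls support training and ask about changes only where these would preclude involvement; AE elicitation is not a stated purpose. Section 10.2 applies to both arms, so controls may report spontaneously. The detection probabilities are assumed, and the simple model cannot return a ratio below 1.

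Most of this stands and limits the point. It does not remove it: section 10.2 does not require an event to have been elicited, and illness or a hospital admission is a natural answer to the question the calls do ask. Part 3 of the working relaxes the assumption of no reporting by controls, and the direction holds as long as weekly contact brings out more than no contact.

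A reader might also infer three stronger things that the documents do not support.

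- That the TSC is the only safety oversight. Section 10.3 sends SAEs, other than the listed expected ones, to the sponsor within one working day, and an annual list of SAEs goes to the ethics committee.
- That the AE counts will inform the larger trial. Section 11.1 says only that results will feed a power calculation for the outcome measures in section 6.2.
- That the recorded rates are biased by a known amount. The schedule shows unequal opportunity to report, not how many events each route will capture.

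**Conclusion.** Following the plan as written gives the two arms unequal opportunity for AEs to be recorded: about 9-13 scheduled post-baseline contacts against 1. Recorded AEs are therefore liable to be more complete in the training arm, and descriptive counts by arm could suggest harm from training where none exists.

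The size is not derivable from the documents. The ratio of 1.04-1.70 rests on assumed capture of 30-70% at the visit and 10-30% on calls, with no reporting by controls between visits; it shrinks if recall at follow-up is good or controls volunteer events. The figure of 240-480 extra calls rests on 60-80 participants and 1:1 allocation. No endpoint or planned test is affected. This is a minor point, worth acting on because the correction is cheap.

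**What to change.** 1. Add a how-detected field to the AE form: weekly call, follow-up visit, spontaneous report, other.
2. At the existing follow-up visit, put the same scripted AE question, covering the time since randomisation, to both arms.
3. State that any AE summary by arm, including one shown to the TSC, uses events elicited by that question.
4. List all other events separately, by arm and route of detection, so that none is lost to safety review. Include there the events of withdrawn participants who do not attend follow-up.

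The cost is one CRF field, one scripted question and a slightly longer visit; no calls or visits are added. Two limits remain. The by-arm summary omits withdrawn participants who do not attend (section 8.9). Having discussed an event on a call may also help trainees recall it at follow-up, so the common question reduces the imbalance without removing it. Both limits should be stated wherever AEs are shown by arm.

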#### Patient consent procedure

Informed consent will be undertaken by either [name] (researcher) or an appropriately qualified research delivery officer at the LPT research delivery team. This will take place in the most convenient location for the participant including; their home, memory service, dedicated research space at the LPT, or invited to the Cerebral

Haemodynamics in Ageing and Stroke Medicine (CHiASM) research space.

Both participants who have capacity, and those that lack capacity will be suitable for inclusion in this study. In cases where the participant lacks capacity, a friend, relative or carer will act as a personal consultee to consent on behalf of the participant. Please see section 14.1 for more information on the ethical code of practice for the inclusion of adults lacking capacity in this study.

The participant or personal consultee must personally sign and date the latest approved version of the informed consent form before any study specific procedures are performed.

The qualitative arm of the study will be consented alongside the feasibility RCT. All participants will be offered to take part in the qualitative arm of the study. Participants will be consented at enrolment into the RCT to be contacted at later date to discuss the option of the qualitative study. Participants that completed the RCT and all assessments will be suitable for inclusion in the qualitative study, and their carers will also be invited to participate. Qualitative study specific information will be provided by the researcher alongside information for the feasibility RCT at study enrolment.

Written and verbal versions of the participant information and Informed consent will be presented to the participants/personal consultee detailing no less than: the exact nature of the study; the implications and constraints of the protocol; the known side effects and any risks involved in taking part. It will be clearly stated that the participant is free to withdraw from the study at any time for any reason without prejudice to future care, and with no obligation to give the reason for withdrawal.

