#### 8.9 Discontinuation/Withdrawal of Participants from Study Treatment

Each participant has the right to withdraw from the study at any time. In addition, the investigator may discontinue a participant from the study at any time if the investigator considers it necessary for any reason including:

Ineligibility (either arising during the study or retrospective having been overlooked at screening)

Significant protocol deviation

An adverse event which requires discontinuation of the study or results in inability to continue to comply with study procedures

Disease progression which requires discontinuation of the study or results in inability to continue to comply with study procedures  
Consent withdrawn  
Lost to follow up

If the participant is withdrawn due to an adverse event, the investigator will arrange for follow-up visits or telephone calls until the adverse event has resolved or stabilised. If a participant has been withdrawn from the study, they will not be required to attend any further assessments or follow-up. Participants who have withdrawn from the study will be included in the data analysis (intention to treat analysis) and will be consented to do so. In the healthy volunteer arm, as this is a feasibility study, withdrawn participants will not be replaced. The reason for withdrawal will be recorded in the CRF.

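### Randomised participants who withdraw without naming an adverse event miss the only scheduled adverse-event enquiry (minor gap, cheap to close)

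*Combined protocol and SAP*

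**What the plan says.** **When AEs are asked about.** Section 8.6 describes the return visit after 8-12 weeks and adds: "Adverse events will also be assessed at this time point". No other time point is named. In Appendix C the row "Adverse event assessments" carries a single mark, under Follow-up.

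**What happens on withdrawal.** Section 8.9 says of withdrawn participants that "they will not be required to attend any further assessments or follow-up". It makes one exception: "If the participant is withdrawn due to an adverse event, the investigator will arrange for follow-up visits or telephone calls", continuing until the event has resolved or stabilised. It also states: "The reason for withdrawal will be recorded in the CRF". Withdrawn participants stay in the analysis (8.9, 11.7).

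**Whether a reason must be given.** Under section 8.3 (Patient consent procedure), participants are told they may leave at any time, "with no obligation to give the reason for withdrawal".

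**Capture outside the visit.** Section 10.2 requires AEs during the study to be recorded on the CRF, whether or not attributed to the study, if the investigator observes them or the participant reports them. It foresees that a participant may "voluntarily withdraw from the study due to what he or she perceives as an intolerable AE".

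**Oversight.** There is no DSMC. AEs are reviewed at the Trial Steering Committee (TSC) meetings (16.2), which are six-monthly (16.1).

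**The concern.** The exception in section 8.9 works only if someone already knows that an AE caused the withdrawal. The plan expects some people to leave because of an AE they find intolerable (10.2), yet lets them leave without saying so (8.3). It schedules no question at the point of leaving that would bring the event to light. A person who leaves for an unrelated reason, but who also had an AE, is likewise never asked.

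What is at stake is the completeness of the harms record that the TSC sees. Two groups rely most on volunteered reports:

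- Waiting-list controls, who have no scheduled contact between baseline and follow-up.
- Participants lacking capacity, whom section 14.1 expects to enrol and for whom a spontaneous report is a weak substitute for a direct question.

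Section 10.3 starts the SAE reporting clock at discovery or notification, so an event nobody learns of starts no clock.

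**Working it through.** The plan states no figure on this point: no withdrawal rate, no AE rate and no AE analysis. The check is mainly a reading of sections against each other, with one simple calculation for scale.

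**Step 1. Follow each type of leaver through the plan.**

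| Situation | Scheduled AE enquiry? | Other route to capture |
|---|---|---|
| Completes to follow-up | Yes (8.6, Appendix C) | 10.2 throughout |
| Withdraws, AE known to be the cause | Visit not required, but AE followed by visit or telephone (8.9) | 10.2 |
| Withdraws, no AE named, intervention arm | None | 10.2; weekly calls until withdrawal |
| Withdraws, no AE named, control arm | None | 10.2 only |

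The last two rows are the gap.

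**Step 2. Check the possible backstops.**

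- *Reason for withdrawal in the CRF (8.9).* It helps only if a reason is given, and a non-medical reason does not show whether an AE also occurred.
- *Weekly calls (8.6, Appendix C).* Their stated purpose is to solve software or programme problems and pick up changes in circumstance. At one call a week for 8-12 weeks, an intervention participant who completes has 8-12 calls; a control has 0. Someone who withdraws early has fewer than the full number.
- *Qualitative interviews.* Section 11.2 invites training-arm participants, including non-completers, but the interviews are optional, stop at saturation and exclude controls. Section 8.3 describes as suitable only those who completed the trial and all assessments. They are not an AE assessment.

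None of these amounts to a scheduled AE question for a withdrawn participant.

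**Step 3. Scale.** Inputs: N = 80 from the synopsis, and N = 60 because sections 11.2 and 14.1 still carry that figure. Section 11.2 describes the 60 as participants needed to complete the programme, so 80 is the better denominator for those randomised. The withdrawal share p is an assumption; the documents give none.

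Number missing the visit, w = p × N:

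| Assumed p | N = 80 | N = 60 |
|---|---|---|
| 5% | 4 | 3 |
| 10% | 8 | 6 |
| 15% | 12 | 9 |
| 20% | 16 | 12 |

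These are upper bounds on the number affected. They count every withdrawal, including those due to a known AE, who are followed under 8.9, and those whose events were observed or volunteered under 10.2. The documents do not allow the remaining subset to be estimated.

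**The case against.** The strongest reply is that the plan already covers most of this. Section 10.2 is a continuous duty, not tied to a visit. Section 8.9 requires the reason for withdrawal to be recorded and AE withdrawals to be followed. Section 9.3 keeps non-adherent participants in the study, so poor compliance alone does not remove anyone from follow-up. Excusing attendance does not forbid asking a question. In the trained arm, a weekly call about circumstances that might end participation comes close to asking why someone is leaving. The residual is then mainly controls who leave unexplained, and who have had no training.

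Much of that stands and is why the point is minor. It does not remove the gap: the remaining capture is passive, and nothing ensures that the question is asked consistently or in both arms.

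A reader might infer more than the documents support:

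- *AEs before week 8-12 go uncollected.* They do not; section 10.2 records observed and reported events throughout.
- *Withdrawn people would be counted as free of AEs because they remain in the analysis.* No text says so, and section 11.5 points the other way: missing data are reported but left out of the final analyses.
- *Unequal telephone contact biases an AE comparison between arms.* Section 11.1 plans no such comparison, and AEs are not an endpoint in section 6.2.
- *Consultee-recruited people withdrawn for distress (14.1) go unrecorded.* Visible distress is arguably an unfavourable sign observed by the investigator, and so already an AE under 10.1.1 and 10.2. Unwillingness without distress does remain within the gap.
- *Section 11.2 implies a dropout of 60 − 50 = 10, or 16.7%.* The 50 is the top of a 24-50 range described as adequate for a feasibility study, not an expected number of completers.

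**Conclusion.** The point holds as a minor gap in harms ascertainment. The single scheduled AE enquiry falls at a visit that withdrawn participants need not attend, and the exception depends on an AE already being known as the cause. At an assumed withdrawal of 5-20%, at most 4-16 of 80 (3-12 of 60) would miss the enquiry. The number with an undetected event would be lower by an amount the documents do not let one calculate.

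No sample size, error rate, efficacy result or feasibility result changes. The case for acting rests on the very low cost, the enrolment of people who lack capacity, and reliance on TSC review of AEs in the absence of a DSMC.

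**What to change.** In section 8.9 and Appendix C, add one standard AE question at the withdrawal contact, for any withdrawal reason and in both arms. Ask the participant or the consultee, with their agreement, by telephone if needed. This leaves intact the right to withdraw without giving a reason.

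Record anyone who declines or cannot be reached as 'AE status not ascertained', and show that count in the AE summary the TSC reviews.

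Nothing more elaborate is needed. With an assumed 3-16 withdrawals spread over two arms and three or four population groups, separate tables for withdrawals would be nearly empty.

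The cost is one question, one response code and a few lines of protocol wording. The downside is a few more minor events to log. Some people will remain unreachable, but the gap will then be visible.
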